#### **4.2 Blood Component Support**

Platelets and RBC support will be given as medically indicated to maintain an adequate hematocrit and to maintain the platelet count at a level of at least 10,000/mm^3 whenever possible. All administered blood products will be irradiated and depleted of leukocytes.

#### **4.3 Other Medications**

With the exception of drugs that would exclude the patient from the protocol (e.g., other investigational anticancer drugs, monoclonal antibodies, chemotherapy, gammaglobulin, drugs that affect lymphocytes), the patients can take other medicines as needed.

### **5 DATA COLLECTION AND EVALUATION**

#### **5.1 Data Collection**

Complete quality assurance records must be maintained on each patient treated on the protocol. These records will be kept by the Research Nurse, and should include copies of primary documentation (e.g., laboratory slips, X-ray reports, scan reports, pathology reports, physician notes, etc.) that demonstrate that:

- The patient met each eligibility criterion;
- The signed informed consent was obtained prior to treatment;
- Treatment was given according to the protocol (dated notes about doses given and reasons for any dose modifications);
- Toxicity was assessed according to protocol (laboratory report slips, etc.);
- Response was assessed according to the protocol (X-ray, scan, lab reports, dated notes on measurements, and clinical assessment, as appropriate); and
- Drug Accountability records were kept for each patient.

#### **5.2 Response Criteria**

##### **5.2.1 Tests required evaluating response**

During the study: follow-up evaluations will be performed at the completion of 2 cycles (4 weeks) of therapy and subsequently after every 4 cycles (8 weeks) thereafter, as outlined in 2.2.1(history and physical examination), 2.2.3 (hematologic, serum studies), 2.2.5 (sIL-2R), 2.2.7 (Urinalysis), 2.2.2 (tumor assessment), and 2.2.13 (flow cytometry) .

After completion of the study treatment: patients will be serially followed monthly or more frequently if clinically indicated. At each monthly visit the patients will undergo the following evaluations, which are defined in Section 2: history and physical examination, hematologic, serum studies, sIL-2R $\alpha$ , Urinalysis, tumor assessment, flow cytometry and if clinically indicated skin biopsy and skin testing which are defined in Section 2.

Follow up: Following the first three months of follow-up patients will be followed at three month intervals for the first year after completion of treatment, every four months for the second year, every six months for the third through fifth year after completion of treatment, and then on a yearly basis. At each quarterly visit the patients will undergo the following evaluations, which are defined in Section 2: history and physical examination, hematologic, serum studies, sIL-2R $\alpha$ , Urinalysis, tumor assessment, flow cytometry and if clinically indicated skin biopsy and skin testing which are defined in Section 2.

#### 5.2.2 Parameters to measure response

Response criteria: From the International Workshop to Standardize Response Criteria for Non-Hodgkin's Lymphoma. Responses must last for at least four weeks off treatment.

##### 5.2.2.1 Complete response (CR)

Complete disappearance of all detectable clinical and radiographic evidence of disease and disappearance of all disease related symptoms if present before therapy and normalization of those biochemical abnormalities (for example LDH) definitely assignable to the lymphoma. All lymph nodes must have regressed to normal size (less than or equal to 1.5 cm in greatest diameter if  $> 1.5$  cm before therapy). Previously involved nodes that were 1.1 to 1.5 cm in greatest diameter must have decreased to less than or equal to 1 cm or by more than 75 percent in the sum of the products of the greatest diameters. The spleen, if considered to be enlarged before therapy, must have regressed in size and not be palpable on physical examination. The bone marrow must show no evidence of disease by histology. Peripheral blood must show a normal pattern by flow cytometry to qualify for a complete remission. Molecular studies will be used to determine response.

##### 5.2.2.2 Complete response unconfirmed (CRUu)

As per complete remission criterion except that if a residual node is greater than 1.5 cm, it must have decreased by greater than 75 percent in the sum of the products of the perpendicular diameters. Lymphocyte aggregates within the bone marrow must be negative for T-cell markers characteristic of adult T-cell leukemia lymphoma.

##### 5.2.2.3 Partial response (PR)

Reduction by  $\geq 50\%$  of leukemia cell count or  $\geq 50\%$  reduction in the size of all measurable lesions, and no increase in size of any measurable or evaluable lesion or appearance of new lesion.

##### 5.2.2.4 Stable disease (SD)

5.2.2.5 Less than a partial response with not more than a 25% increase in leukemia cell count, no new lesions, or less than a 25% increase in any measurable.

##### 5.2.2.6 Progressive disease (PD)

Appearance of new lesions, or an increase of 25% or greater in the sum of the product of the perpendicular diameters of the measurable lesions or persistent (at least two determinations) doubling of the peripheral blood leukemic cell count.

### 5.3 Toxicity Criteria

Toxicity will be assessed according to the NCI Common Toxicity Criteria version 3.0.

A copy of the CTC version 3.0 can be downloaded from

<http://ctep.cancer.gov/reporting/ctc.html>.

All appropriate treatment areas should have access to a copy of the CTC version 3.0

### 5.4 Statistical Section

5.4.1 This study will include patients diagnosed with chronic, lymphomatous or acute ATL. Full lists of inclusion and exclusion criteria are presented in Section 2.2 and 2.3.

5.4.2 We will use an optimal two-stage design {Simon, 1989} to test for early evidence for efficacy based on complete and partial response. The design is based on the following: (a) the response proportion (partial and complete response) will be less than 5% if the treatment is totally ineffective ( $P_0=0.05$ ), (b) the treatment will be considered effective and worthy of future investigation if the true response proportion is  $> 30%$  ( $P_1=0.30$ ), (c) a type I error rate of 5% (i.e., the probability of concluding that the treatment is effective if the true response rate is 5% is 0.05), (d) a power of 95% (i.e., the probability of concluding that the treatment is effective if the true response proportion is 30% is 0.95).

In the first stage of the two-stage design, nine patients will be studied. If there are no partial or complete responses observed among the initial nine patients treated with a dose of 9 mcg/kg/d, the study will be expanded to an additional 9 patients at a dose of 18 mcg/kg/d. If one or more of the nine patients respond at either dose level, the study will proceed to a second stage. An additional 20 patients (i.e., a total of 29 patients in the trial) will be studied in the second stage at the same dose level. If four or more out of the 29 patients respond, the treatment will be deemed effective in early phase II development. The treatment will be deemed ineffective if fewer than four respond out of 29 patients.

With this design, there is a 63% chance of proceeding to the 18 mcg/kg/dose, if the response rate at 9 mcg/kg.dose is an ineffective 5%. Similarly, there is a 63% chance of terminating the study if the response rate at 18 mcg/dose/day is 5%.

The major objective of this study is to determine the anti-tumor activity of Denileukin diftitox with regard to response rate, time to progression, and overall survival. Response rate will be based on the number of patients who achieve either a complete or partial response to therapy. Time to progression will be measured from the date of registration until documentation of disease progression. Overall survival will be determined from the date of registration to the event of death or, for surviving patients, censored by the last day patients are known alive.

5.4.3 Antitumor Efficacy:

Tumor status will be evaluated at pre-treatment, after 2 cycles of therapy, and every 8 weeks on study until the development of a complete remission or evidence of disease progression. Post-study assessment of tumor response will be at four weeks after

completion of therapy and every month for the first three months and then at three month intervals for the first year, four month intervals for the second year, six month intervals for the third through fifth years and then yearly thereafter. The objective tumor response (CR+PR) rate and 95% C.I. will be calculated. For responders, duration of response is measured from the response (CR+PR) to the document disease progression or censored at the latest evaluation. Median duration of response will be calculated using Kaplan-Meier method.

Time to disease progression will be measured from the date of registration until documentation of disease progression. Patients who do not experience disease progression will be censored by last day of evaluation or the latest day with known tumor status prior to being lost to follow-up, or the earliest day when patients receive any new cancer therapies, whichever comes first. Patients who have died without disease progression will also be censored by the day of the last evaluation prior to death. Death without a documented progression will not be considered as an event of disease progression. Overall survival will be determined from the date of registration to the event of death or, for surviving patients, censored by the last day patients known alive. Median time to progression and median of overall survival will be estimated using Kaplan-Meier method.

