### *Design:*

- Nine patients will be treated initially with 9mcg/kg/d of Denileukin diftitox for five days, on an every two week schedule.
- Tumor response will be evaluated after two cycles of treatment. Stable or responding patients will continue treatment with evaluations every four cycles of treatment. Patients will be treated for two cycles beyond a complete remission.
- If no responses are seen at the 9 mcg/kg/d dose, and toxicity is acceptable, an additional 9 patients will be treated at a dose of 18 mcg/kg/d with the same statistical design.
- The trial uses an optimal 2 stage design targeting for a true response proportion > 30%. Nine patients will be treated initially at a dose of 9 mcg/kg/d, with expansion to 29 patients if a response is seen in one of the initial nine patients treated., If no response is seen at the 9 mcg/kg/d dose an additional 9 patients will be treated at a dose of 18 mcg/kg/d with expansion to 29 patients at this dose level if a response is seen. A stopping rule for excessive toxicity will be incorporated.

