#### 1.2.8 Proposed treatment plan

Patients with the chronic, lymphomatous and acute forms of ATL will be treated with 9 or 18  $\text{mcg}/\text{kg}/\text{d}$  for five days of Denileukin diftitox on an every two week schedule. Nine patients will be treated initially with a dose of 9  $\text{mcg}/\text{kg}/\text{d}$  with expansion to 29 patients if a response is seen in one of the nine initial patients treated. If no response is seen at this dose level, and if no excessive toxicity is seen, an additional 9 patients will be treated at a dose of 18  $\text{mcg}/\text{kg}/\text{d}$ . If a response is seen, this dose level cohort will be expanded to 29 patients. Tumor response will be evaluated after two cycles of treatment. Stable or responding patients will continue treatment

with evaluations after every four cycles of treatment for up to a total of 12 months of therapy. Treatment with Denileukin diftitox, beyond the 12 month time period is at the discretion of the Principal Investigator. Patients will be treated for two cycles beyond a complete remission.

Summary of results of treatment with denileukin diftitox at the 9 mcg/kg/d dose

Nine patients were treated at the 9 mcg/kg/d dose but no objective responses were seen. Evidence of anti-tumor activity was observed in leukemic patients where as evidenced by reductions in leukemic blood counts (Appendix 4). Two potential alternatives were considered; first, prolonged infusions at the same dose for 10 days and second, a higher dose of the agent. Denileukin diftitox was well tolerated in all patients with only one grade 3 non-hematologic toxicity of clinical importance, a supraventricular tachycardia associated with a cardiac troponin leak that resolved with medical management and did not recur with rechallenge. The toxicity observed at the 9 mcg/kg/d dose is summarized in Appendix 5. This proposed amendment will evaluate the other FDA approved dose of denileukin diftitox, 18 mcg/kg/d for 5 days, administered on an every other week basis to rule out a 30% response rate.

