## **3 STUDY IMPLEMENTATION**

### **3.1 Study Design**

Patients with the chronic, lymphomatous and acute forms of ATL will be treated with 9 or 18 mcg/kg/d for five days of Denileukin diftitox, on an every two week schedule. Nine patients will be treated initially with a dose of 9 mcg/kg/d with expansion to 29 patients if a response is seen in one of the nine initial patients treated. If no response is seen at this dose level, and if no excessive toxicity is seen, an additional 9 patients will be treated at a dose of 18 mcg/kg/d. If a response is seen, this dose level cohort will be expanded to 29 patients. Tumor response will be evaluated after the initial two cycles of treatment. If patients are stable or responding, they will continue treatment with evaluations after every four cycles of treatment for a period of 12 months in total. If patients have achieved a complete remission they shall be treated with a further two cycles of consolidation therapy.

The study will be conducted in accordance with the procedures established by CBER and FDA

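### Does the 5% type I error in Section 5.4.2 understate the false-positive risk, given that two dose levels may be tested in turn?

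*Combined protocol and SAP*

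**What the plan says.** Section 5.4.2 specifies a Simon optimal two-stage design. The response proportion "will be less than 5% if the treatment is totally ineffective" (p0 = 0.05), and "the treatment will be considered effective and worthy of future investigation if the true response proportion is" above 30% (p1 = 0.30). Type I error is set at 5%, defined as "the probability of concluding that the treatment is effective if the true response rate is 5% is 0.05", and power at 95%.

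Nine patients are treated first at 9 mcg/kg/d. With no response, nine new patients are treated at 18 mcg/kg/d. "If one or more of the nine patients respond at either dose level, the study will proceed to a second stage", with 20 more patients at that same dose. "If four or more out of the 29 patients respond, the treatment will be deemed effective in early phase II development". The section also gives the probability of no response in nine at a 5% rate, 63%, separately for each dose.

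The Precis, under Design, says that after no response at the lower dose "an additional 9 patients will be treated at a dose of 18 mcg/kg/d with the same statistical design". Section 3.1 attaches a second condition to opening the higher dose: "If no response is seen at this dose level, and if no excessive toxicity is seen". Section 5.4.5 plans 29 patients if the trial completes at 9 mcg/kg/d and 38 if it completes at 18 mcg/kg/d.

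Section 1.2.8 reports the lower dose's result: "Nine patients were treated at the 9 mcg/kg/d dose but no objective responses were seen".

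**The concern.** The 5% is defined by an event, the conclusion that the treatment works, and the plan lets that conclusion be reached by two routes. An ineffective drug gets one chance at 9 mcg/kg/d and, if nobody among the first nine responds, a second at 18 mcg/kg/d. Read as a statement about the whole trial, 5% is then too low. Section 5.4.2 works out the chance of moving on to the second dose but gives no error rate for the sequence, and it does not say that 5% and 95% belong to one dose.

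At stake is how a positive result is read. If success were declared at 18 mcg/kg/d, it would come from the second of two planned tests of the same drug, and someone relying on the 5% might think it covered the whole search.

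**Working it through.** **Inputs.** From Section 5.4.2: p0 = 0.05, p1 = 0.30, 9 patients in stage 1, continue with at least 1 response, 20 more in stage 2, success with at least 4 of 29. From the Precis: the same design at the second dose. From Section 1.2.8: 0 of 9 at 9 mcg/kg/d.

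**Step 1. Reproduce the plan's figures for one dose.** The probability of declaring success at true rate p is

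R(p) = sum over x from 1 to 9 of P[Bin(9, p) = x] × P[Bin(20, p) ≥ 4 − x].

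At p = 0.05:

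| Stage 1 responses | Probability | Chance of reaching 4 in total | Product |
|---|---|---|---|
| 1 | 0.29854 | 0.07548 | 0.02253 |
| 2 | 0.06285 | 0.26416 | 0.01660 |
| 3 | 0.00772 | 0.64151 | 0.00495 |
| 4 or more | 0.00064 | 1 | 0.00064 |

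The unrounded sum is R(0.05) = 0.0447. The same sum at p = 0.30 gives R(0.30) = 0.9519. No response in nine at 5% has probability 0.95^9 = 0.6302, the stated 63%. A search over designs with up to 40 patients returns this rule as the Simon optimal design for error at most 5% and power at least 95% (expected size 16.4 patients under p0). All the stated figures therefore hold for one dose.

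**Step 2. Both doses, before the trial.** With true rates p9 and p18,

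error over both doses = R(p9) + (1 − p9)^9 × R(p18).

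With p18 = 0.05:

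| p9 | R(p9) | (1 − p9)^9 | Error over both doses |
|---|---|---|---|
| 5% | 0.04473 | 0.6302 | 0.0729 |
| 4% | 0.02222 | 0.6925 | 0.0532 |
| 3% | 0.00854 | 0.7602 | 0.0425 |
| 2% | 0.00205 | 0.8337 | 0.0393 |
| 1% | 0.00016 | 0.9135 | 0.0410 |

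The maximum over all pairs of rates up to 5% is 7.29%, with both at 5%. The total passes 5% only when p9 is above about 3.8%, or above about 4.4% if both doses share one rate.

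The toxicity condition can only lower it. If the higher dose were allowed to open with probability q (an assumption, taken as independent of response), the maximum is 0.04473 + q × 0.02819, where 0.02819 = 0.6302 × 0.04473. That gives 7.0% for q = 0.9 and 6.7% for q = 0.8.

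The second dose also raises power: with both rates at 30%, 0.9519 + 0.0404 × 0.9519 = 0.990.

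**Step 3. After the observed 0 of 9.** The first term of the Step 2 formula has gone: the lower dose stopped at stage 1. The 18 mcg/kg/d cohort consists of new patients, so at a given true rate its result does not depend on the 0 of 9. The remaining error is R(0.05) = 4.47% and the remaining power is R(0.30) = 95.19%.

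**The case for a change.** The strongest case for an amendment is that the defined event is a conclusion about the treatment, not about a dose; that 7.29% is 2.29 points above the stated 5%, nearly half as much again; that Section 1.2.8 was updated with the 0 of 9 while Section 5.4.2 still describes the lower dose as to come; and that a few sentences would settle it at no cost to patients or timelines. Asking for the label is not the same as asking for multiplicity control.

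The arithmetic stands, and so does the absence of the words 'per dose level'. The inference to an amendment does not. Error and power are inputs to a Simon design, and such a design describes one passage from 9 to 29 patients. The plan runs that passage at either dose, keeps stage 2 within a dose, quotes 63% for each dose separately, and calls the second run the same design. The sequence is fully disclosed, and no sentence claims 5% control over both doses. An analyst would take the error rates as per dose, and they are correct on that reading.

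Reporting a positive 18 mcg/kg/d result alongside 7.3% would make matters worse. Of the 7.29 points, 4.47 are false claims at 9 mcg/kg/d, which the 0 of 9 has ruled out. A false claim at 18 mcg/kg/d had probability 0.6302 × 0.0447 = 2.8% before the trial and has 4.5% now. Neither figure is 7.3%.

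**Conclusion.** No change is needed. The 5% and 95% are correct for the rule at each dose level (exact values 4.5% and 95.2%), so there is no error of calculation, only an unstated label that the rest of the text supplies. The two-dose error was up to 7.3% at the design stage, and only near the edge of the null: both true rates at 5%, every response-eligible opening of the higher dose permitted by toxicity. A modest excess of this kind in exchange for trying a second dose is a fair trade in an early phase II screen that claims no control across doses.

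For the plan as it now stands, the question has closed. With 0 of 9 at the lower dose, the only remaining test has 4.5% error and 95.2% power, inside what Section 5.4.2 promises. The threshold of 4 in 29, the sample size and the conclusion drawn from them are the same with or without the label. This rests on the two cohorts being separate patients, as the plan describes, and on the rule being followed as written. Anyone quoting 7.3% should present it as a design-stage figure, not as the error rate of an 18 mcg/kg/d result.

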### **3.11 Off Study Criteria**

- 3.11.1 Patient noncompliance or request to withdrawal from the study  
3.11.2 Tumor progression and initiation of another treatment.  

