3.11.3 Completion of the protocol follow up period  
3.11.4 Death

### **3.12 Post-Treatment Evaluation (Follow-up)**

- 3.12.1 After completion or discontinuation of the study treatment, the patients will be serially followed monthly for the first three months and then at three month intervals unless the patient begins treatment for their ATL under the care of another physician.

At these interval visits, the patients will undergo the following evaluations which are described in Section 2:

- history and physical examination
- hematologic, serum studies
- sIL-2R $\alpha$
- Urinalysis
- tumor assessment
- flow cytometry

3.12.2 If clinically indicated patients shall undergo the following studies which are described in Section 2:

- skin biopsy
- skin testing.

3.12.3 Patients shall undergo apheresis on completion of therapy and the sample processed by Lab of Cellular Oncology for DNA microarray

3.12.4 After the first year the patients shall be followed every four months for the second year, every six months for the third through fifth year after completion of treatment, and then on a yearly basis.

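### Duration of response lacks the censoring at new cancer therapy that the same section applies to time to progression, so time on a later agent can be counted in it

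*Combined protocol and SAP*

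**What the plan says.** All references are to the combined protocol and SAP.

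- **Duration of response (5.4.3).** For responders, "duration of response is measured from the response (CR+PR) to the document disease progression or censored at the latest evaluation". There are two outcomes only, and the median is estimated by Kaplan-Meier.
- **Time to progression (5.4.3, next paragraph).** For patients without progression, the censoring dates include "the earliest day when patients receive any new cancer therapies, whichever comes first".
- **Follow-up (3.12.1).** Visits are monthly for three months and then "at three month intervals unless the patient begins treatment for their ATL under the care of another physician". Each visit includes tumor assessment. The follow-up schedules in 5.2.1 and 5.4.3 do not mention a stop at new therapy.
- **Off study (3.11.2).** The criterion reads "Tumor progression and initiation of another treatment".
- **Response (5.2.2 and 5.4.2).** "Responses must last for at least four weeks off treatment". The rate counts complete and partial responses: "Response rate will be based on the number of patients who achieve either a complete or partial response to therapy".
- **Decision rule (5.4.2).** Nine patients, then 29 if at least one responds; success is four or more responses in 29. Duration of response plays no part in it.

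**The concern.** Both endpoints use the same patients and the same tumor assessments. The plan treats the start of another cancer therapy as the end of interpretable follow-up for one endpoint and ignores it for the other.

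Study drug can stop without progression: two cycles after a complete remission, at 12 months (both 3.1), or for toxicity, in which case 3.3 keeps the patient on study for follow-up. If such a responder then starts another therapy with the same team, tumor assessment continues. The duration-of-response rule then takes the latest progression-free visit as the censoring date, even when the patient has been on a different agent for months.

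Two things are at stake. The duration reported for denileukin diftitox can include time on another agent. And the two results for one patient can disagree, with a response reported as lasting beyond the point at which time to progression stopped counting.

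**Working it through.** **1. The plan's own figures, and whether this point touches them.** Inputs from 5.4.2: response rates 0.05 and 0.30, 9 then 20 further patients, success at 4 or more of 29.

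- Early stop at 5%: 0.95^9 = 0.630 (plan: 63%).
- P(success) = sum over x = 1 to 9 of P(Bin(9, p) = x) × P(Bin(20, p) ≥ 4 − x).
- At p = 0.05 this is 0.0447 (limit 0.05). At p = 0.30 it is 0.952 (plan: 95%).

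The design reproduces. Duration of response appears in none of these formulas, so changing its censoring rule leaves them as they are.

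**2. The two rules for one patient.** The dates are assumed, in months from registration: response at 2, study drug stopped at 4, new therapy from the same team at 5, last visit at 17 with no progression.

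| Endpoint | Rule | Result |
|---|---|---|
| Time to progression | as written | censored at 5 |
| Duration of response | as written | censored at 17 − 2 = 15 |
| Duration of response | with the time-to-progression rule | censored at 5 − 2 = 3 |

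Both durations are censored values, not observed lengths. As written, the response runs to month 17, which is 12 months past the censoring of time to progression.

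**3. What one such patient can do to a small Kaplan-Meier median.** Assume five responders, four of whom progress at 4, 6, 8 and 10 months after response. Take the median as the first time at which the estimate is 0.5 or less.

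- Fifth patient censored at 15: the estimate is 0.8 at 4, 0.6 at 6 and 0.4 at 8. The median is 8.
- Fifth patient censored at 3: four are at risk at month 4, and the estimate is 0.75 at 4 and 0.50 at 6. The median is 6.

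**4. What switching could do on average.** The documents give no rate of switching and no effect of later therapy, so every input here is an assumption. Take exponential response durations with a 4-month median (the figure in 1.2.6 for cutaneous T-cell lymphoma). Let a fraction w of those still in response at 2 months switch then, and let the new therapy multiply their remaining time by k. Without censoring at the switch, for t > 2:

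S(t) = 2^(−1/2) × [(1 − w) × 2^(−(t−2)/4) + w × 2^(−(t−2)/(4k))]

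Setting S(t) = 0.5 gives the median in months:

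| w | k = 1 | k = 2 | k = 3 |
|---|---|---|---|
| 10% | 4.0 | 4.1 | 4.2 |
| 20% | 4.0 | 4.2 | 4.3 |
| 30% | 4.0 | 4.4 | 4.6 |
| 50% | 4.0 | 4.7 | 5.1 |

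With censoring at the switch, the median stays at 4.0 throughout, because switching in this model is unrelated to prognosis. If the later therapy does nothing (k = 1), there is no bias.

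**The case against.** **The route is narrow.** It needs a responder who has stopped study drug, has not progressed, starts a new therapy and is still seen by the study team. For treatment under another physician, 3.12.1 ends scheduled follow-up, so the latest evaluation would normally fall at or before the switch. The off-study item in 3.11.2 is terse; if either event alone were enough, the route would close further. This stands as a limit on how often the problem arises. It does not close the gap: 3.12.1 leaves out treatment by the study team, and 3.11.2 as worded joins the two events.

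**Duration of response is secondary.** Section 5.4.2 lists response rate, time to progression and overall survival under the major objective. Duration of response is descriptive. This stands too, and it limits the weight of the point.

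**A reader might infer that the response rate is inflated as well**, since 5.2.2 does not define the treatment that a patient must be off, and one miscounted response could turn 3 of 29 into 4 of 29. The documents do not support that. The rate in 5.4.2 counts response to therapy, 4.3 excepts chemotherapy, monoclonal antibodies and other investigational anticancer drugs from permitted medicines, and 5.2.2 asks that a response persist off treatment. No text says that a response maintained by another agent counts. At 9 mcg/kg/d, 1.2.8 reports falls in leukemic counts and still no objective responses in nine patients. What remains is a missing clarification, not a demonstrated error.

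**A reader might also point to the 11 of 19 responses to interferon and AZT in 1.2.4.2** as a measure of the bias. They show that another ATL therapy can be active. They say nothing about how many responders here would switch or for how long their response would be extended, and the same section gives a whole-group median survival of only 3 months.

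**Conclusion.** The point holds in limited form. Section 5.4.3 has a new-therapy censoring rule for time to progression and a stated rule for duration of response that omits it. Applied as written, the second rule can count progression-free time on another agent as denileukin diftitox response, and can contradict the same patient's time to progression.

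That the effect of later therapy will be credited to the study drug is a stronger claim that the text does not bear out. It is possible for a responder who switches without progression under the study team, and largely prevented for one treated elsewhere.

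The size cannot be derived from the documents. The shifts of 0.1 to 1.1 months in step 4 (for k = 2 and 3) and of 2 months in the five-patient example rest entirely on assumed inputs. The success rule of 4 in 29, the attained type I error of 0.0447 and the power of 0.952 are not affected.

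**What to change.** In 5.4.3, censor duration of response by the rule already used for time to progression: at the earliest day the patient receives any new cancer therapy, if progression has not been documented before then. Use the same date and the same scope (any new cancer therapy) for both endpoints, so that the section does not end up with two different switching rules. The wording should also cover a patient who switches first and progresses later.

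As a minor clarification in 5.2.2, state that tumor assessments made after a new cancer therapy begins are not used to establish or confirm a complete or partial response.

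The cost is one sentence in each section. Therapy start dates are already needed for time to progression, so no new data item is required, and sample size, error rates and treatment do not change. The downside is that the reported duration of response may be shorter and more heavily censored. As with time to progression, censoring at a switch assumes that switching is unrelated to prognosis, so the number of responders censored for this reason should be reported beside the median.
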